### **9.2.3 Suspected Unexpected Serious Adverse Reaction Definition**

An SUSAR is a suspected unexpected serious adverse reaction. In order to be qualified as a SUSAR, the AE must meet 3 criteria: the event is serious, there is a certain degree of probability that the event is a reaction to the study drug being researched and the nature and severity of the reaction are not in agreement with the product information (ie, the reaction is unexpected as per the reference safety information). All SUSARs will be reported as required to the Competent Authorities and to the Ethics Committee (EC)/Institutional Review Boards (IRBs) of the countries and centers concerned.

### **9.2.4 Adverse Events of Special Interest**

### **9.3 Assessment of Adverse Events**

The Investigator is responsible for assessing the severity and causality of AEs.

#### **9.3.1 Assessment of Severity (Intensity) of Adverse Events**

On the AE eCRF, the Investigator will use the adjectives MILD, MODERATE, or SEVERE to describe the maximum intensity of the AE. For purposes of consistency, these intensity grades are defined as follows:

- MILD: Does not interfere with subject's usual function.
- MODERATE: Interferes to some extent with subject's usual function.
- SEVERE: Interferes significantly with subject's usual function.

As described previously in [Section 9.2.2](#), note the distinction between the severity and the seriousness of AE. A severe event is not necessarily a serious event. For example, a headache may be severe (interferes significantly with subject's usual function) but would not be classified as serious unless it met one of the criteria for SAEs, listed above in [Section 9.2.2](#).

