Subjects will receive QR-110 as a unilateral IVT injection in their worse eye (see [Section 4.2.1.2](#)). Treatment of the worse eye is common practice in the development of ophthalmic products ([Bainbridge 2008](#), [Ghazi 2016](#), [Jacobson 2012](#), [Maguire 2009](#)). Unilateral injection serves as an additional means to ensure safety, as visual function is driven by a subject's better eye. Unless otherwise specified, both safety and efficacy evaluations

-will be based on the assessment of the treatment eye in comparison to baseline measures and to the untreated eye (referred to hereafter as the contralateral eye). As there is no approved therapy for the treatment of LCA due to the *CEP290* p.Cys998X mutation, no suitable comparator currently exists. The contralateral eye, therefore, serves as a control and removes the biases due to the absence of a relevant comparator, or the

administration of placebo by IVT injection, which is considered unethical in this population. Assessments based on both the comparison of the treatment eye to the contralateral eye, and changes from baseline in the treatment eye will provide the strongest comparisons from which to evaluate safety and efficacy data.

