#### **3.3 Exploratory Objective**

### **4.0 STUDY OVERVIEW**

#### **4.1 Criteria for Evaluation**

##### **4.1.1 Primary Endpoint**

- Frequency and severity of ocular AEs in the treatment and contralateral eyes

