7.1 Study/Treatment Eye Definition and Unit of Analysis

The study eye will be the treated eye for all efficacy and safety summaries. The study eye will always be referred to as the treated eye on TLFs and is defined as the eye with the worse visual acuity at

Screening. If both eyes have the same visual acuity, the Investigator should determine the eye with the worse visual function, according to other measures of ophthalmic function (FST or mobility course score). If the visual function is the same per the Investigator's assessment, then the treated eye will be determined at Investigator discretion.

The unit of analysis for all ocular endpoints will be the eye level. All ocular endpoints will be summarized by eye and by dose group and cohort (ie, adult versus pediatric) for the treated eye and contralateral eye where appropriate. Subject level information, non-ocular AEs, medical history,-

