Additional summaries of TEAEs will be provided showing the number and percentage of subjects who experienced at least one TEAE. These summaries will be presented by system organ class (SOC) and preferred term (PT). Non-ocular TEAEs will be summarized using discrete summary statistics and presented by dose group at the subject and event level by SOC and PT. Ocular TEAEs will be similarly summarized at the subject level for study and contralateral eyes separately. If the same PT is reported for a subject multiple times within the same SOC, that PT will only be reported once within that SOC. As with the PT, if multiple conditions within the same SOC are reported, that SOC will only be reported once. In the summary, SOC will be listed in ascending alphabetical order; PTs will be listed in order of descending frequency for all subjects within each SOC. The occurrence of non-ocular and ocular TEAEs will also be tabulated by SOC and PT for the following: maximal severity and suspected relationship to study drug.

Separate summaries will be provided for the following categories of AEs:

- All AEs
- Ocular TEAEs in the treated eye and contralateral eye (includes treatment-related events)
- Non-ocular TEAEs (includes treatment-related events)
- TEAEs leading to treatment discontinuation
- TEAEs leading to subject withdrawal or treatment discontinuation
- Serious TEAEs (SAEs)
- TEAEs by maximum severity
- TEAEs by maximum relationship
- TEAEs of special Interest

Severity of an AE is defined as a qualitative assessment of the degree of intensity of an AE as determined by the Investigator or reported to him/her by the subject. The assessment of severity is made

irrespective of relationship to study drug or seriousness of the event and should be evaluated according to the following scale:

- *Mild*: Does not interfere with subject's usual function.
- *Moderate*: Interferes to some extent with subject's usual function.
- *Severe*: Interferes significantly with subject's usual function.

Summaries of TEAEs by maximal severity will be presented for ocular AEs and non-ocular AEs separately. The number of subjects with any TEAEs (along with percentages) will be tabulated by SOC and PT within each SOC by dose group. To count the number of subjects with any TEAEs, if a subject has multiple TEAEs coded to the same PT within the same SOC, the subject will be counted once under the maximal severity.

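### AE severity is graded on whole-subject function, so visual loss confined to the treated (worse) eye may be graded lower than the same loss in the contralateral eye

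*Protocol*

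**What the plan says.** The primary endpoint (Protocol 4.1.1) is "Frequency and severity of ocular AEs in the treatment and contralateral eyes". Protocol 9.3.1 gives one severity scale for all AEs, ocular or not. It runs from "MILD: Does not interfere with subject's usual function" to "SEVERE: Interferes significantly with subject's usual function". SAP 12.1 repeats it ("Does not interfere with subject's usual function" for the lowest grade) and adds no ocular anchor in the readable text. The grade is then tabulated: "Summaries of TEAEs by maximal severity will be presented for ocular AEs and non-ocular AEs separately".

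The treated eye, in SAP 7.1, "is defined as the eye with the worse visual acuity at" Screening. If acuity is equal, the Investigator decides on other measures of function and then at discretion. Protocol 2.3.1 gives a safety reason for treating one eye only: "Unilateral injection serves as an additional means to ensure safety, as visual function is driven by a subject's better eye". The same section names the contralateral eye as a control.

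**The concern.** The scale asks what an event does to the subject. The endpoint asks how bad events are in each eye. These can part company when the injected eye is the one that contributes less to vision. The feature that protocol 2.3.1 counts as protection, that harm to the worse eye costs little visual function, can also keep such harm from registering on a scale that measures only function.

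The tilt would have a direction, because the treated eye is the worse eye by rule and not by chance. Two things would be at stake: a reader setting severity in the treated eye against severity in the control eye could see the treated eye in too favourable a light, and a substantial loss in the treated eye could appear in the table simply as Mild.

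**Working it through.** The plan has no figure to reproduce: the sample size rests on no power calculation (Protocol 10.2), and no AE rate or distribution of acuity gaps is given. The check is one of logic, with a small calculation to show direction and limits.

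**Inputs**
- Best acuity allowed in the contralateral eye: +0.4 logMAR (Protocol 5.3.1, criterion 2).
- Worst acuity allowed in the treated eye: light perception (same criterion), assigned 4.0 logMAR in SAP 14.1.
- Equal acuity is allowed (Protocol 4.2.1.2, SAP 7.1).
- A change of 0.3 logMAR equals 15 letters (SAP 14.1), so 15 / 0.3 = 50 letters per logMAR.

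**Range of the gap**
Largest: 4.0 − 0.4 = 3.6 logMAR. Smallest: 0, at a tie.

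**Effect of the same loss in either eye**
Assume, taking Protocol 2.3.1 literally, that visual function follows the acuity of the better-seeing eye, V = min(T, C), where T and C are the baseline logMAR of the treated and contralateral eyes. Let g = T − C ≥ 0, and let one eye lose d.
- Loss in the treated eye: min(T + d, C) − C = 0, whatever d is.
- Loss in the contralateral eye: min(T, C + d) − C = min(g, d).

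The difference between eyes is therefore min(g, d).

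| Gap g | Loss d | Change in V, treated eye affected | Change in V, contralateral eye affected |
|---|---|---|---|
| 0 | 0.6 (30 letters) | 0 | 0 |
| 0.4 | 0.6 (30 letters) | 0 | 0.4 (20 letters) |
| 3.6 | 0.6 (30 letters) | 0 | 0.6 (30 letters) |
| 0.4 | 0.3 (15 letters) | 0 | 0.3 (15 letters) |

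The second row is an assumed subject within eligibility, with the treated eye at 1.0 and the contralateral eye at 0.6. If the treated eye goes from 1.0 to 1.6, the better-seeing eye stays at 0.6, and the literal definition of Mild can be met. If the contralateral eye goes from 0.6 to 1.2, the better-seeing eye is now the treated one at 1.0, a fall of 0.4 × 50 = 20 letters, and a higher grade is plausible. Which grade an Investigator would actually choose cannot be computed from the documents.

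**Do other parts of the plan supply the eye-level anchor?**
Flare (SAP 12.2.1), lens opacity (12.2.2), vitreous haze (12.3), IOP (12.4) and BCVA (14.1) are recorded by eye, and the BCVA listing flags changes of at least 0.3 logMAR. Examination dates are matched to the dates of AEs of special interest. In the readable text none of these sets the severity grade or is shown beside it.

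**The case against.** A reader might infer that all treated-eye events are under-graded and that the severity part of the endpoint is biased as a matter of fact. The documents do not support that.
- Protocol 2.3.1 speaks of visual function; the scale speaks of usual function. Protocol 9.3.1 uses headache as its example of a severe event, so non-visual interference counts. Pain, photophobia or inflammatory symptoms in the worse eye can still be Moderate or Severe.
- Symptom-free findings, such as a raised IOP that the subject does not notice, would be Mild in either eye, so they create no difference between eyes.
- At equal acuity the calculation gives no difference.
- Frequency, the other part of the endpoint, does not depend on the grade.
- This SAP is descriptive, and the contralateral eye receives no injection, so for injection-related events the same event in both eyes is largely hypothetical.
- The signal is not lost. Eye-level findings are tabulated or listed by eye, preferred terms for reduced acuity and blindness count as events of special interest, and seriousness is assessed separately from severity (Protocol 9.2.2).

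A reader might also infer that the grade distorts decisions to stop treatment. Protocol 4.2.2.1 lists severity as one of several considerations and provides for ongoing review of ophthalmic safety data. Nothing readable makes the grade decisive. The definitions of events of special interest (Protocol 9.2.4, SAP 12.1.1) and Table 3 of the protocol are not in the text available, so nothing is concluded from them.

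All of this stands and narrows the point. It does not supply an eye-level anchor for the severity grade, nor put the eye-level findings next to it for every ocular TEAE.

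**Conclusion.** The concern holds as a limited, directional risk. For visual-loss events confined to one eye, the stated scale may give a lower grade when that eye is the treated one. The size is bounded by the smaller of the loss and the acuity gap, and the gap can be anything from 0 to 3.6 logMAR. That rests on two assumptions: that visual function tracks the better-seeing eye, as the protocol says, and that Investigators apply the scale literally. The number of events affected cannot be estimated from the documents. The consequence is that the severity table, read alone, is not a sound comparison between eyes. Since severity by eye is part of the primary endpoint and the data to put this right are already collected, the change is worth making.

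**What to change.** In SAP 12.1, add a table or listing beside the ocular TEAE table by maximal severity. For each ocular TEAE, by eye, show the findings collected between onset and resolution: BCVA change from baseline with the flag for 0.3 logMAR or more, flare grade, vitreous haze grade, lens opacity grade and IOP. Add a note that the severity grade reflects whole-subject function and should not be read alone as a comparison between eyes.

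This needs no new data and extends the date matching that the SAP already plans for events of special interest. The cost is one extra output, and some treated-eye events graded Mild may be shown with substantial eye-level change.

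Rewriting the scale in Protocol 9.3.1 to refer to the affected eye is not the remedy for this trial. SAP 7.6 places all 11 subjects in the second interim analysis and times the third to the last subject's final visit. A new scale would mix two gradings or require events to be regraded in retrospect.

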### 9.3.2 Assessment of the Relationship of Adverse Events to Study Drug

The Investigator will make a causality assessment about the relationship of each AE to study drug. To ensure consistency of AE and SAE causality assessments, Investigators should apply the following general guideline:

**Not Related:** The AE has an etiology other than the study drug (eg, preexisting medical condition, underlying disease, intercurrent illness, or concomitant medication); and/or the AE has no plausible temporal relationship to administration of the study drug (eg, cancer diagnosed 2 days after first dose of study drug).

**Possibly Related:** An AE that follows a reasonable temporal sequence from administration of the study drug, follows a known or expected response pattern to the study drug, but that could readily have been produced by a number of other factors.

**Probably Related:** An AE that is clearly related to the study drug or its administration (ie, an event that follows a reasonable temporal sequence from administration of the study intervention, follows a known or expected response pattern to the suspected intervention, that is confirmed by improvement on stopping and reappearance of the event on repeated exposure and that could not be reasonably explained by the known characteristics of the subject's clinical state).

**Definitely Related:** The AE is clearly related to the study drug; a re-challenge confirms the association (not required or desirable in some circumstances but provides strong evidence when it happens).

For all AEs and SAEs, Investigators will make separate assessments of causality about the relationship of the event to study drug and to drug administration (ie, IVT injection).

**Note:** The Investigator's assessment of causality for individual AE reports is part of the study documentation process and will be recorded in the subject's medical record, AE eCRF, and SAE form if applicable. Adverse events recorded without the Investigator's assessment of the relationship to study drug will be followed up until causality is assigned.

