## 2.2.2 Clinical Experience

No clinical studies have been conducted with QR-110 Solution for IVT Injection.

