## **10.0 STATISTICAL METHODOLOGY**

### **10.1 General Considerations**

A comprehensive Statistical Analysis Plan (SAP) specifies the statistical methodology, and table, listing and figure (TLF) formats for all aspects of the planned analyses. The SAP supports the completion of the Clinical Study Report (CSR) for this protocol. As the risk profile of QR-110 in humans is unknown and this is a first-in-human trial, all AEs will be considered in determining the safety profile of QR-110 unless obviously unrelated. As an early phase clinical study, exploratory analyses not necessarily identified in the SAP may be performed to support the clinical development program. Any p values that will be calculated according to the analysis plan will be interpreted in view of the exploratory nature of the study. Any post-hoc, or unplanned, analyses not identified in the SAP will be clearly identified in the CSR, in accordance with applicable Standard Operating Procedures (SOPs) of the sponsor.

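### The causality scale makes a recognised reaction pattern a condition of both middle grades, so in this first-in-human study an uncertain novel event has no proper grade

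*Protocol*

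**What the plan says.** Protocol 9.3.2 sets four grades.

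- *Not Related*: the event has another cause, and/or its timing is implausible.
- *Possibly Related*: the event has reasonable timing and "follows a known or expected response pattern to the study drug, but that could readily have been produced by a number of other factors" (joint conditions).
- *Probably Related*: the event is clearly related to the drug or its administration, has reasonable timing, "follows a known or expected response pattern to the suspected intervention", is "confirmed by improvement on stopping and reappearance of the event on repeated exposure", and is not reasonably explained by the subject's clinical state.
- *Definitely Related*: the event is clearly related, and the text adds "a re-challenge confirms the association (not required or desirable in some circumstances but provides strong evidence when it happens". No pattern is required.

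The section calls these definitions a general guideline whose purpose is consistency. It also requires that an event without a causality grade be followed up until one is given. SAP 12.1 repeats the four definitions and says that investigators were instructed to use them.

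Protocol 2.2.2 states: "No clinical studies have been conducted with QR-110 Solution for IVT Injection". Protocol 10.1 calls the human risk profile unknown and says that "all AEs will be considered in determining the safety profile of QR-110 unless obviously unrelated". Under Protocol 10.6.1 an event counts as drug-related if it is graded at least *Possibly* or if the grade is missing. Protocol 9.2.3 requires, for a suspected unexpected serious adverse reaction (SUSAR), some probability of a drug reaction and that "the nature and severity of the reaction are not in agreement with the product information".

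**The concern.** A first-in-human study has to pick up reactions that nobody has described yet. The two grades meant for uncertain cases both ask whether the event looks like something already known or anticipated. An investigator who follows the text with a new and uncertain event finds no grade that fits, yet must enter one.

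If the entry is *Not Related*, these provisions lose the event:

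- the drug-related TEAE tables (Protocol 10.6.1);
- follow-up of drug-related events that persist beyond 90 days after the last dose (Protocol 9.4.1);
- immediate telephone notification of fatal or life-threatening events attributed to the drug (Protocol 9.5);
- reporting of serious events that arise after participation and are thought possibly related (Protocol 9.5).

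The wording also sits badly with two neighbouring rules. Protocol 10.1 sets a much lower bar for counting an event towards the safety profile. Protocol 9.2.3 depends on investigators suspecting the drug in events that are not in the reference safety information.

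**Working it through.** The plan gives no figure to reproduce. The check takes one event through the four definitions. The event has plausible timing, no recognised pattern, no established other cause and no re-exposure result, and the investigator is unsure of the cause.

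| Grade | Conditions as written | Does the event meet them? |
|---|---|---|
| *Not Related* | Another cause, and/or implausible timing | No, neither limb applies. Lack of a known pattern is not a ground for this grade. |
| *Possibly* | Timing, and pattern, and other factors could readily explain it | No, it fails on pattern, even where other factors are conceivable. |
| *Probably* | Clearly related, timing, pattern, improvement on stopping, recurrence, no reasonable clinical explanation | No, it fails on pattern and on recurrence. |
| *Definitely* | Clearly related; re-challenge confirms but is not always needed | Only if the investigator already judges it clearly related, and here the investigator is unsure. |

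The event meets no grade.

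**Order of the grades.** *Probably* and *Definitely* both start from a clear relationship. *Probably* then requires pattern and recurrence. *Definitely* requires no pattern and allows re-challenge to be absent. On both counts the lower grade is the stricter one.

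**Missing grades.** Protocol 10.6.1 counts a missing grade as drug-related. That is not a dependable fallback, because Protocol 9.3.2 has missing grades chased until one is assigned.

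**Weight of one event.** Protocol 4.2.1.4 sets at least 2 subjects per cohort, with one adult and one paediatric cohort per dose level, so at least 2 + 2 = 4 per dose level. SAP 2.3 and Section 3 say that only the low and mid doses were used. SAP 7.6 refers to 11 subjects in all. If every subject was dosed and each cohort reached its minimum, a dose group has between 4 and 11 − 4 = 7 subjects. Moving one subject in or out of the related column changes the percentage by:

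- 1/7 = 14.3 points to 1/4 = 25.0 points within a dose group;
- 1/11 = 9.1 points over all subjects.

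**Check of the remedy.** Suppose *Possibly* means plausible timing where a drug cause cannot be excluded. The test event is then *Possibly Related*. With recurrence removed and pattern only supportive, *Probably* no longer asks for more than *Definitely* on either count.

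**The case against.** Four stronger conclusions are tempting, and the documents do not support them.

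1. A reader might infer that a novel reaction can be graded as related only after re-challenge. That is wrong. *Definitely* has no pattern condition and says that re-challenge is not always needed. It helps only where the investigator is already convinced.
2. A reader might infer that the protocol sends novel events to *Not Related*. It does not, since that grade needs another cause or implausible timing. Misfiling there is a prediction about behaviour.
3. A reader might infer that no expected pattern can exist for a new drug. The condition is met by a known or an expected pattern, and the Investigator's Brochure, animal studies or experience with other intravitreal oligonucleotides could supply one. The brochure is not available here. The protocol does not say whether such sources count as expectation for this purpose, so investigators may differ.
4. A reader might infer that the scale and the SUSAR definition exclude each other. Protocol 9.2.3 does not refer to the four grades, and an event can follow an anticipated pattern yet be unexpected in severity or absent from the reference safety information.

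It is also fair to say that the main safeguards do not use the grade. The primary endpoint counts all ocular events (Protocol 4.1.1), and the overall TEAE tables have no relatedness filter. All serious events are reported within 24 hours whatever the cause (Protocol 9.5), and the data monitoring committee reviews all safety data (Protocol 4.2.2.2). With up to four doses planned, and with doses that may be held rather than stopped, recurrence could sometimes be seen. The injection procedure has its own causality assessment, and the definitions are only a guideline.

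These points limit the reach of the problem. They do not give the uncertain novel event a grade.

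**Conclusion.** The concern holds as a faulty rule of limited reach. Both middle grades require a recognised pattern in a study whose drug has an unknown human risk profile, and *Probably* is stricter than *Definitely*. What can be lost is confined to the relatedness tables and to the follow-up and reporting steps that depend on causality.

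The number of events affected cannot be derived from the documents and may be zero. The weight of each is large because the study is small (12 subjects planned, at most 18). The 14.3 to 25.0 point range rests on the stated assumptions about dosing and cohort size.

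The conclusion assumes that investigators apply the definitions as written. If they treat the guideline loosely, the grades may be sensible but will not be consistent between sites, and consistency is the scale's stated purpose. The sponsor should correct this before the relatedness tables are relied on.

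**What to change.** **Protocol 9.3.2.** Define *Possibly Related* as plausible timing where a drug cause cannot be excluded. Make a known or expected pattern supporting evidence, not a condition, for both *Possibly* and *Probably*. Remove the recurrence condition from *Probably*, so that the grades run in order. This brings the scale into line with Protocol 10.1 and 9.2.3.

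**SAP 12.1.** Keep describing the scale actually used. Events have already been graded on it and interim analyses have been run (SAP 7.6), so rewriting the definition would not regrade anything and would misdescribe the data. Add a sensitivity drug-related table that also counts TEAEs graded *Not Related* with plausible timing and no documented alternative cause, shown beside the table based on the investigator's grade. If any events are graded after a protocol change, identify which scale applied to each.

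**Cost.** This takes a wording change, one small table and a review of the *Not Related* events. The review may need source records, because Protocol 9.5 asks for a causality rationale for serious events and Protocol 8.1 lists no such item for the rest. With this few subjects the burden is small. Somewhat more events will be counted as possibly related.

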## **10.6 Safety Analyses**

### **10.6.1 Treatment Emergent Adverse Events**

A treatment emergent AE (TEAE) is defined as an event that was not present prior to administration of the first dose of study drug and present after the first dose or if it represents the exacerbation of an event that was present prior to the first dose.

Adverse events noted during the study will be coded to system organ classes (SOCs) and preferred terms (PTs) using the Medical Dictionary for Regulatory Activities (MedDRA) dictionary. The overall incidence of TEAEs will be summarized by dose group and classified by SOC and PT. Deaths, AE severity, seriousness, relationship to study drug and study discontinuation due to AE will also be tabulated by dose group. An AE will be considered drug-related if the Investigator indicated the event is at least “possibly” related or if the relationship is missing. Adverse events with missing start dates, but with stop dates overlapping into the treatment period will be counted as treatment emergent. All AEs will be listed in subject listing, and summarized by numbers and percentages of subjects by dose for each portion of the study separately. If a subject reports the occurrence of a particular event more than once, the most severe of those events will be included in the summary tables of TEAEs, and the most severe of the treatment-related events will be included in the summary tables of TEAEs.

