The Investigator will make a causality assessment about the relationship of each AE to study drug. To ensure consistency of AE and SAE causality assessments, the Investigators were instructed to apply the following general guideline:

- *Not Related*: The AE has an etiology other than the study drug (e.g., preexisting medical condition, underlying disease, intercurrent illness, or concomitant medication); and/or the AE has no plausible temporal relationship to administration of the study drug (e.g., cancer diagnosed 2 days after first dose of study drug).
- *Possibly Related*: An AE that follows a reasonable temporal sequence from administration of the study drug, follows a known or expected response pattern to the study drug, but that could readily have been produced by a number of other factors.
- *Probably Related*: An AE that is clearly related to the study drug or its administration (i.e., an event that follows a reasonable temporal sequence from administration of the study intervention, follows a known or expected response pattern to the suspected intervention, that is confirmed by improvement on stopping and reappearance of the event on repeated exposure and that could not be reasonably explained by the known characteristics of the subject's clinical state).
- *Definitely Related*: The AE is clearly related to the study drug; a re-challenge confirms the association (not required or desirable in some circumstances but provides strong evidence when it happens).

For all AEs and SAEs, Investigators will make separate assessments of causality about the relationship of the event to study drug.

All TEAEs will be presented in a subject listing. The TEAEs leading to study treatment discontinuation will be listed separately. In addition, all serious AEs will be presented in a separate listing.

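### One grade of the study-drug causality scale also covers administration of the drug, so an injection reaction that recurs can be rated either Probably Related or Not Related to drug

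*Protocol*

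**What the plan says.** Protocol 9.3.2 introduces the scale as a rating against the drug: "The Investigator will make a causality assessment about the relationship of each AE to study drug". Of the four grades, *Possibly Related* and *Definitely Related* name the study drug as the suspected cause. *Not Related* applies when "The AE has an etiology other than the study drug", or when the timing is implausible. *Probably Related* is the exception. It opens "An AE that is clearly related to the study drug or its administration" and then speaks of an intervention rather than of the drug. Among its conditions is one on recurrence: "that is confirmed by improvement on stopping and reappearance of the event on repeated exposure".

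The same section requires "separate assessments of causality about the relationship of the event to study drug and to drug administration (ie, IVT injection"). The protocol therefore intends two ratings per event.

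SAP 12.1 reproduces the four grades, including the administration wording, but its version of the last requirement ends early: "Investigators will make separate assessments of causality about the relationship of the event to study drug". The SAP tabulates TEAEs by "maximal severity and suspected relationship to study drug", and also by maximum relationship. Its text describes no table by relationship to the injection.

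The counting rule is in Protocol 10.6.1: "An AE will be considered drug-related if the Investigator indicated the event is at least" possibly related, or if the relationship is missing.

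**The concern.** A drug scale that lets in the procedure at one grade cannot be applied uniformly to procedural events. Two investigators who agree fully that the injection caused an event could grade it on opposite sides of the drug-related cut, each following the text.

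This matters more here than in a sham-controlled trial. Neither sham nor placebo injections are given (Protocol 2.3.1), so a difference between treated and contralateral eye reflects drug and procedure together. Injection complications are expressly AEs (Protocol 9.2.1). Each subject has up to four injections (Protocol 4.2.1.4), so an event has the chance to recur. Investigator causality is one of the few ways to separate drug from procedure, alongside comparison of the dose levels in very small groups. What is at stake is the meaning of the drug-related TEAE tables.

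A table by relationship to the injection would not be enough alone. The drug rating would stay ambiguous.

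**Working it through.** The plan states no figure on this point. The check is a comparison of text, followed by simple division for scale.

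**Step 1. The grades side by side (Protocol 9.3.2; same grades in SAP 12.1).**

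| Grade | Cause named | Counted as drug-related (Protocol 10.6.1) |
|---|---|---|
| Not Related | something other than the study drug | No |
| Possibly Related | study drug | Yes |
| Probably Related | study drug or its administration | Yes |
| Definitely Related | study drug | Yes |

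**Step 2. A test case.** Take an event caused by the injection procedure that resolves and returns after a later injection.

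- *Not Related*: the cause is other than the drug, so the general wording is met. The listed examples do not mention the procedure, but they are only examples.
- *Probably Related*: administration is named. The timing, the expected pattern, the improvement and the reappearance on repeated exposure can all be met, and the subject's clinical state need not explain the event.

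Both grades fit.

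**Step 3. A one-off reaction.** The recurrence condition is not met, so *Probably Related* does not clearly apply. The overlap is limited to recurrent reactions.

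**Step 4. Route to the tables.** Recurrent AEs are recorded individually (Protocol 9.4.3, item b), and the SAP summarises by maximum relationship. One later occurrence rated *Probably Related* is enough to place the subject there.

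**Step 5. Scale.** Change in drug-related incidence when one subject crosses the cut = 1/N, provided that the subject has no other event counted as drug-related.

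| Denominator | Source | Change |
|---|---|---|
| 11 | all subjects at interim analysis 2, SAP 7.6 | 1/11 = 9.1 points |
| 12 | planned, Protocol 10.2 | 1/12 = 8.3 points |
| 18 | maximum, Protocol 10.2 | 1/18 = 5.6 points |

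By dose group, the SAP reports two dose levels in use (2.3 and section 3). If each level has its minimum of 2 adults and 2 pediatric subjects, a group has at least 4 and, of 11, at most 11 − 4 = 7. The change is then between 1/7 = 14.3 and 1/4 = 25.0 points. The actual split is not given. Neither is the number of subjects with a recurrent procedural event, so no total effect can be computed.

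**The case against.** The strongest reply is that the protocol already rates the injection separately, so a procedural event has its proper place. On this view the references to an intervention show one generic scale serving both ratings, and the grades are only a general guideline. The eCRF guide and the Study Reference Manual, which may settle practice, are not available. This reply stands in part: practice may be better than the text. But the opening sentence ties the scale to study drug, and a scale meant for both ratings would not mention administration in one grade of four. The SAP, read alone, does not mention an injection rating.

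A second reply is that rewording leaves another route open. An event that might be due to drug or procedure can still be rated *Possibly Related* and counted. That is correct, and the fix does not claim otherwise. That grade expresses real doubt about cause. The defect here concerns events whose procedural cause is not in doubt.

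A third reply is that the present wording errs towards attributing events to the drug, which is cautious in a first-in-human study. This also stands as a cost of changing it.

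A reader might go further and infer three things that the documents do not support:

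- **That all injection reactions are counted as drug effects.** The recurrence condition excludes one-off reactions from any clear fit, and the result depends on which overlapping grade the investigator picks.
- **That dose-escalation decisions are distorted.** Protocol 4.2.2.2 has the DMC and the Sponsor Medical Monitor weigh the totality of safety data, and SAP 7.5 supplies safety listings. Nothing ties a decision to drug-related incidence.
- **That the drug-related incidence could lie anywhere from 0% to 100%.** That is the full possible range of a proportion and says nothing about this trial.

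**Conclusion.** The scale is internally inconsistent. Under the written rules, an injection reaction that resolves and recurs can be graded on either side of the drug-related cut, so drug-related TEAE tables can include recurrent procedural events. Each such subject is worth 9.1 points of all-subject incidence at N = 11, or 8.3 at N = 12, assuming no other drug-related event in that subject and, for the first figure, that the 11 subjects in the SAP are the treated denominator. How many subjects are affected is unknown.

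The reach is limited. The primary endpoint, frequency and severity of ocular AEs in both eyes (Protocol 4.1.1), does not use causality. Protocol 10.1 considers all AEs in the safety profile unless obviously unrelated. A post-injection pressure rise, the obvious example, is also summarised by eye and visit, including immediately after dosing, and as an event of special interest by preferred term (SAP 12.4), whatever its causality grade. The point deserves correction because the affected tables are planned outputs and the wording change is small. It does not undermine the trial's main safety result.

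**What to change.** 1. In Protocol 9.3.2 and SAP 12.1, delete *or its administration* from *Probably Related*, and replace *study intervention* and *suspected intervention* with *study drug*.
2. State that the injection is rated on the same four grades, with *IVT injection* in place of *study drug*.
3. In SAP 12.1, restore the missing half of the separate-ratings sentence, so that it again covers drug administration as the protocol does.
4. For events already recorded, keep the ratings and report drug-related TEAEs cross-classified by the recorded injection rating. This assumes that the injection rating was collected as the protocol requires.
5. Do not query only the events rated *Probably Related* to drug and also related to the injection. In an open-label trial with interim analyses already done, such queries could mainly lower drug ratings. If ratings are reviewed, review every injection-related AE whatever its drug grade, and report both the recorded and the revised counts.

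The cost is a wording change in two documents and a little extra tabulation. The downside is that drug-related counts may be slightly lower, and so less conservative, than under the present wording.
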